## Analysis of non-serious treatment emergent adverse events

• All non-serious TEAEs by primary SOC and PT presented in alphabetical order within each SOC with PT >5% in any treatment arm.

## Analysis of product complaints

- Number (%) of patients experiencing product complaints;
- Number (%) of patients experiencing product complaints associated with a TEAE;

#### 2.4.5.2 Deaths

The following summaries of deaths will be generated for the safety population.

LDL-C <25 mg/dL (respectively <15 mg/dL) will be considered.

- Number (%) of patients who died by study period (on-study, on-treatment, post-study);
- Deaths in non-randomized patients or randomized but not treated patients
- Treatment-emergent AEs leading to death (death as an outcome on the AE e-CRF page as reported by the Investigator) by primary SOC and PT showing number (%) of patients sorted by internationally agreed SOC order, with PT presented in alphabetical order within each SOC. TEAE leading to death are TEAE that led to death regardless of timing of death in relation to IMP injection (i.e., death occurring in the TEAE period or during the post-treatment period).
- All deaths will be listed, with reason.

#### 2.4.5.3 Analyses of laboratory variables

The summary statistics (including number, mean, standard deviation, median, Q1 and Q3, minimum and maximum) of all laboratory variables (central laboratory values and changes from baseline) will be calculated for each visit or study assessment (baseline, each post-baseline time point of the treatment period, last on-treatment and/or worst on-treatment) by treatment group. In addition, for some parameters of interest, mean changes from baseline with the corresponding SE will be plotted over time (at same time points) in each treatment group. This section will be organized by biological function as specified in Section 2.1.4.3. For glucose, only fasting samples will be summarized.

The incidence of PCSAs (list provided in Appendix A) at any time during the TEAE period will be summarized by treatment group whatever the baseline level and/or according to the following baseline status categories:

26-Apr-2017

- Normal/missing
- Abnormal according to PCSA criterion or criteria

For parameters for which no PCSA criteria are defined, similar table(s) using the normal range will be provided.

If any clinically significant signal is detected and needs further characterization, exploration of time to onset will be performed for selected PCSAs assessed during the TEAE period as described below to account for the differential exposure time in all patients.

The incidence rates of selected PCSA during TEAE period at 24 weeks of exposure will be calculated with Kaplan-Meier methodology, using the midpoint of the time interval between the first assessment with PCSA and the previous assessment. Kaplan-Meier curves will be also provided. Only the first event (PCSA) will be counted. Patients without any event will be censored at the last assessment performed during the TEAE period.

#### Hepatitis C antibody

The number and percentage of patients with a post-baseline seroconversion for hepatitis C test will be provided by treatment group in post-baseline period (including the TEAE and post-TEAE periods) as well as in the TEAE period alone. Post-baseline seroconversion is defined for patients with a negative baseline status who had either a "positive ribonucleic acid" (RNA) or a "confirmed positive antibody (Ab) with negative RNA", a "confirmed positive antibody (Ab) with no RNA available" post-baseline status as defined in the table below. Other situations require case by case evaluation and will be described individually if relevant.

The status as regards to hepatitis C virus (HCV) for a patient will be defined as described for all evaluations (baseline and post-baseline).

1st Ab **Positive** Negative RNA Positive Missing Negative Missing Positive Negative Negative Negative . Negative / 2nd Ab Any result Positive Negative Missina Positive Anv result Positive Positive missing missing missing Conf. Negative Positive Positive Conf. **HCV** Positive Positive positive RNA. Ab no Positive Ab no infection Negative Negative Negative Ab no Negative **RNA** Ab with conf. Ab RNA RNA RNA status RNA neg. RNA missing available available available

Table 1 - Definition of the patient status regarding hepatitis C virus

The baseline evaluation will be based on tests performed during the pre-treatment period.

If no Ab test is available or with "indeterminate" as result pre-treatment or post-baseline, respectively, the RNA test (if available) will be used alone to determine the status of the patient. If no RNA is available then the hepatitis C status of the patient will be missing.

Property of the Sanofi Group - strictly confidential

26-Apr-2017

## Drug-induced liver injury

The liver function tests, namely AST, ALT, ALP and total bilirubin, are used to assess possible drug-induced liver toxicity. The proportion of patients with PCSA values or ALT increase as defined in AESI section (see Section 2.1.4.1) at any post-baseline visit by baseline status will be displayed by treatment group for each parameter.

An evaluation of drug-induced serious hepatotoxicity (eDISH) with the graph of distribution of peak values of ALT versus peak values of total bilirubin will also be presented using post-baseline values during TEAE period. Note that the ALT and total bilirubin values are presented on a logarithmic scale. The graph will be divided into 4 quadrants with a vertical line corresponding to 3 x ULN for ALT and a horizontal line corresponding to 2 x ULN for total bilirubin.

Listing of possible Hy's law cases identified by treatment group (i.e., patients with any elevated ALT >3 x ULN, and associated with an increase in bilirubin >2 x ULN, concomitantly or not) with AST, ALT, ALP, GGT, total bilirubin, and if available, direct and indirect bilirubin will be provided.

The incidence of liver-related TEAEs will be summarized by treatment group. The selection of PTs will be based on SMQ Hepatic disorder (see Section 2.3.5.1). Time to liver-related treatment discontinuation will be analyzed using Kaplan-Meier estimates presented by treatment group.

#### 2.4.5.4 Analyses of vital sign variables

The summary statistics (including number, mean, standard deviation, median, Q1 and Q3, minimum and maximum) of all vital signs variables (raw values and changes from baseline) will be calculated for each visit or study assessment (baseline, each post-baseline time point of the treatment period, last on-treatment and/or worst on-treatment and follow-up visit) by treatment group. In addition, for some parameters of interest, mean changes from baseline with the corresponding SE could be plotted over time (at same time points) in each treatment group.

• The incidence of PCSAs at any time during the TEAE period will be summarized by treatment group.

If any clinically significant signal is detected and needs further characterization, exploration of time to onset will be performed for selected PCSAs assessed during the TEAE period as described below to account for the differential exposure time in all patients.

The incidence rates of selected PCSA during TEAE period at 24 weeks of exposure will be calculated with Kaplan-Meier methodology, using the midpoint of the time interval between the first assessment with PCSA and the previous assessment. Kaplan-Meier curves will be also provided. Only the first event (PCSA) will be counted. Patients without any event will be censored at the last assessment performed during the TEAE period.

### 2.4.5.5 Analyses of electrocardiogram variables

Not applicable.

Property of the Sanofi Group - strictly confidential

26-Apr-2017

## 2.4.5.6 Additional safety analyses: region North America

Additional safety analyses on selected endpoints will be replicated in the subgroup of patients of the region North America.

## 2.4.7 Analyses of diabetes-related endpoints

The analyses of diabetes-related endpoints will be performed on the ITT population and will be descriptive only. Summary statistics, including the mean, SD, median, Q1 and Q3, minimum, and maximum of the 3 endpoints (HbA1c, FPG, and number of glucose lowering treatments, see Section 2.1.9) will be calculated for each visit and presented by treatment group, for the raw values as well as the change from baseline. The analysis will be performed overall and by randomization stratum as per IVRS (for strata with at least 10% of patients) and also in the subgroup of patients of the region North America.

#### 2.4.8 Analyses of anti-alirocumab antibody variables

The following summaries will be performed on the ADA population (see Section 2.3.3), taking into account all samples regardless of timing in relation to injections:

- ADA status (negative or positive) by time point and by treatment group and also according to up-titration status;
- Neutralizing status (negative or positive) by time point for positive ADA and by treatment group and also according to up-titration status;
- ADA titers using descriptive statistics (median, minimum and maximum) for positive ADA by time point and by treatment group and also according to up-titration status;
- Number (%) of patients with pre-existing ADA and number (%) of patients with treatment-emergent ADA positive response by treatment group, overall and according to up-titration status;

26-Apr-2017

Number (%) of patients with persistent/transient/intermediate treatment-emergent ADA

Version number: Final

26-Apr-2017

• Time to onset of treatment-emergent ADA positive response using descriptive statistics by treatment group, overall and according to up-titration status.

positive response by treatment group, overall and according to up-titration status;

Correlations between ADA parameters (e.g., titers, treatment-emergent ADA positive status, neutralizing status) and safety and/or efficacy endpoints will be also explored (e.g., box plot, scatter plot).

Additional analyses of ADA parameters may also be replicated in the subgroup of patients in the region North America.

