## 10.6.2.1 Allergic adverse event with cutaneous involvement

Adverse events with cutaneous involvement which are obviously of allergic origin or injection site reactions which progress/expand/worsen/etc should be evaluated by a dermatologist as soon as possible, and preferably within one week of the site first becoming aware of the event.

The Investigator should evaluate the patient for possible etiologies (new medications, etc) and extracutaneous symptoms and signs. An unscheduled assessment for hematology, chemistry, liver panel should be obtained. An additional blood sample will have to be drawn for pharmacokinetics (PK) and anti-alirocumab antibody analyses (adequate instructions will be provided to the site by the Monitor). If it is possible, the site will take pictures of the skin lesions in order to provide the patient with them for the dermatologist's visit. If the photos are obtained, then copies should be kept as source documents which may later be collected by the sponsor. The Investigator will provide a summary of the patient's case, reason for consultation, and information being requested to the consulting dermatologist.

A full consultation report should be sent by the dermatologist to the Investigator. The full report should contain, at a minimum, the following information; a detailed description of the rash (such as the morphology [lesion type], shape of individual lesions, arrangement of multiple lesions [eg, scattered, grouped, linear], distribution, color, consistency, presence of pruritus or pain, and other clinical signs) and in case a skin biopsy (including histopathology and immunofluorescence) was done (if it was deemed necessary as per the dermatologist's or Investigator's medical judgment), the results of this investigation with, if applicable, a specific diagnosis of the AE. The Investigator will fax the full report and the corrected AE form if necessary, to the Monitoring Team Representative within 24 hours.

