#### 2.1.10 Anti-alirocumab antibodies

Anti-alirocumab antibodies (status, neutralizing status and titer) will be collected at Week 0, Week 12, and Week 24.

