# 2.3.3 Anti-alirocumab antibody population

The ADA analysis will be performed on safety population with a blood sample for antibodies at Week 0 (baseline) and at least one evaluable blood sample for antibodies post-baseline.

Property of the Sanofi Group - strictly confidential

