#### 2.5.3 Windows for time points

Data analyzed by time point (including efficacy data, laboratory safety data, vital signs, PCSK9, diabetes-related parameters, ADA) will be summarized using the analysis windows given in Table 2 - Analysis windows definition. These analysis windows will be applicable for all analyses, and they are defined to provide more homogeneous data for time point-specific analyses.

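### Antibody samples triggered by allergic events can bias the exploratory ADA–allergy association upward

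*SAP*

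**What the plan says.** SAP 2.1.10 sets the schedule: "Anti-alirocumab antibodies (status, neutralizing status and titer) will be collected at Week 0, Week 12, and Week 24". That gives each patient two planned post-baseline reads.

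Protocol 10.6.2.1 covers adverse events with cutaneous involvement that are clearly allergic, and also injection-site reactions that get worse: "injection site reactions which progress/expand/worsen/etc should be evaluated by a dermatologist as soon as possible". For these it requires more blood: "An additional blood sample will have to be drawn for pharmacokinetics (PK) and anti-alirocumab antibody analyses".

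SAP 2.4.8 builds its ADA summaries by "taking into account all samples regardless of timing in relation to injections". They include patient-level results: "number (%) of patients with treatment-emergent ADA positive response by treatment group, overall and according to up-titration status", the persistent, transient or intermediate class, and time to onset. The same section then plans: "Correlations between ADA parameters (e.g., titers, treatment-emergent ADA positive status, neutralizing status) and safety and/or efficacy endpoints will be also explored". The examples given are box plots and scatter plots. No test, alpha level or particular safety endpoint is named.

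SAP 2.3.3 admits a safety-population patient who has a baseline sample and "at least one evaluable blood sample for antibodies post-baseline". SAP 2.5.3 adds: "Data analyzed by time point (including efficacy data, laboratory safety data, vital signs, PCSK9, diabetes-related parameters, ADA) will be summarized using the analysis windows".

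**The concern.** If event-triggered samples count towards treatment-emergent status, the number of opportunities to be found positive depends on the outcome that ADA status is later compared with. A patient without a reaction is read twice after baseline; a patient with one can be read three times. An extra read can turn a never-positive patient into an ever-positive one, but never the reverse, so any distortion runs towards an association between antibodies and allergy. It can also bring forward the observed onset date in patients who reacted.

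Evaluating antibody development is a stated secondary objective, and SAP 2.4.8 is where the plan looks at whether antibodies go with safety events. A plot showing more ADA among patients with reactions would be read as clinical information, although part of the pattern could come from how often those patients were sampled.

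**Working it through.** The plan states no ADA rate, ADA duration or rate of triggering events, so there is no figure to reproduce. The calculations below assume **no true link** between ADA and allergy and ask what one extra sample does. All ADA rates, durations and trigger rates are assumptions.

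**Inputs from the documents.** Two scheduled post-baseline reads, at Days 85 and 169 (SAP 2.1.10 and the Table 2 target days); one extra read per triggering event (Protocol 10.6.2.1); 280 alirocumab patients (SAP 1.1).

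**1. Independent positives.** If each sample is positive with probability q, independently, then P(ever positive in k samples) = 1 − (1 − q)^k.

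| q | k = 2 | k = 3 | ratio |
|---|---|---|---|
| 1% | 1.99% | 2.97% | 1.49 |
| 2% | 3.96% | 5.88% | 1.48 |
| 5% | 9.75% | 14.26% | 1.46 |

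This is the unfavourable end when both scheduled samples are present. If one scheduled sample is missing, the comparison is two reads against one: [1 − (1 − q)²]/q = 2 − q, or 1.98 at q = 2% and 1.95 at q = 5%.

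**2. A time course.** Let ADA onset be uniform over the 168 days, with transient ADA lasting D days (D ≤ 84), and let the extra read fall on a random day. The two scheduled reads detect a fraction 2D/168. The extra read adds (1 − 2D/168) × D/168. The ratio simplifies to 1.5 − D/168:

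- D = 28: 0.333 rises to 0.444, ratio 1.33
- D = 56: 0.667 rises to 0.778, ratio 1.17
- D = 84: everything is already detected, ratio 1.00

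If half of responses are persistent and the rest last 28 days, detection goes from 0.5 + 0.5 × 0.333 = 0.667 to 0.5 + 0.5 × 0.444 = 0.722, ratio 1.08. If all are persistent, the Day 169 sample detects every one and the ratio is 1.00. Simulation gave the same values. A ratio of 1.00 for ever-positive status does not protect time to onset, which an extra read can still shorten.

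**3. Patients involved.** If 3% of 280 (8 patients) have a triggering event, the expected number ADA-positive among them rises from 0.32 to 0.47 at q = 2%, and from 0.78 to 1.14 at q = 5%. If 5% (14 patients) do, it rises from 0.55 to 0.82, or from 1.37 to 2.00.

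No test is planned. As a gauge only, a nominal 5% Fisher test under independent positives would reject in 4.8–8.2% of trials across these scenarios, against 1.9–2.5% with equal sampling.

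**4. Between-arm incidence.** Protocol section 4 reports injection-site reactions in 6.2% of alirocumab patients in earlier studies. Even if every one of these triggered a sample, at q = 5% the arm's ADA incidence would move by 0.062 × (0.1426 − 0.0975) = 0.0028, or 0.28 percentage points.

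**The case against.** The main counter-argument is that the plan may not count these samples at all. The clause on timing concerns dosing: Protocol 9.2.5.2.1 asks for pre-dose samples, and the clause naturally means that a sample is kept whatever its relation to an injection. It does not mention unscheduled or event-triggered draws. SAP 2.1.10 lists only Weeks 0, 12 and 24. SAP 2.5.4, which allows unscheduled values, names efficacy, safety laboratory data and vital signs but not ADA. For PCSK9, SAP 2.4.9 explicitly brings in unscheduled measurements; SAP 2.4.8 has no such wording. The text available does not define treatment-emergent ADA. This stands as far as it goes: inclusion of the extra samples is the literal reading of all samples, not a certainty. It also means that two programmers could derive the status differently.

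By-time-point tables are largely protected, since SAP 2.5.3 takes one value per window, nearest the target day. That does not reach patient-level status, class or onset.

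A reader might infer that the plan creates a spurious association. The documents do not support that: the bias can be nil, the trigger is narrow, and the analysis is exploratory and graphical, with allergy not named as the endpoint. A reader might also infer that the comparison of ADA incidence between arms is distorted. The shift is at most about 0.3 percentage points on the figures above, and Protocol 10.6.2.1 does not limit the extra sample to one arm, so that inference should not be pressed.

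Finally, restricting the ADA population or the main incidence table to scheduled samples has its own risk. Under Protocol 10.3.3 and 10.3.4, patients with serious or severe related hypersensitivity stop treatment, and those who then decline further visits may have only an unscheduled end-of-treatment assessment. Excluding them could remove the worst reactions. That objection stands, and the fix leaves both as written.

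**Conclusion.** The point holds as a possible upward bias in an exploratory analysis. Protocol 10.6.2.1 ties extra ADA sampling to allergic events, SAP 2.4.8 excludes no samples, and the resulting status is compared with safety endpoints.

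For one extra sample with both scheduled samples present, the apparent ratio under no true link lies between 1.00 and about 1.5. The lower end applies if ADA persists or lasts 84 days or more; the upper end needs independent positives or very short-lived ones. It approaches 2 only if a scheduled sample is also missing. These figures rest on assumed ADA rates and durations, and on the literal reading of SAP 2.4.8. The primary and key secondary efficacy analyses are not affected.

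**What to change.** In SAP 2.4.8:

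- State that the ADA status used in the ADA–safety correlations is derived from the scheduled Week 0, 12 and 24 samples.
- List event-triggered ADA results separately, alongside the event that prompted them.
- Keep the all-samples ADA incidence, and add a scheduled-only display of treatment-emergent incidence and time to onset as a sensitivity analysis.

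Leave the ADA population in SAP 2.3.3 unchanged.

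With both scheduled samples present, every patient in the correlations then has the same two post-baseline reads, and the ratio due to unequal sampling is 1.00 by construction.

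The cost is a short addition to the SAP text, one listing and one sensitivity display. The downside is that transient positives seen only at the time of the event leave the correlation plots and appear only in the listing and the all-samples table.

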	I 08. On stable dose of medications that are known to influence weight and/or lipids (other than LMTs) within 3 months prior to the screening visit or during the screening period (eg, estrogen replacement, oral steroids, antipsychotics known to impact weight).
	I 09. Signed written informed consent.
	Exclusion criteria:
	
 
Use of any LMTs other than statins within 4 weeks prior to the screening visit or during the screening period (eg, ezetimibe, fenofibrate, nicotinic acid, omega-3 fatty acids, etc) or use of over the counter products/nutraceuticals known to impact lipids (eg, red yeast rice) within 4 weeks prior to the screening visit or during the screening period.
 

	
 
Currently drinking more than 2 standard alcoholic drinks/day (Note: A standard drink is considered as 1 pint/bottle of beer, 1 glass of wine, or 1 shot of hard liquor).
 

	
 
Body Mass Index (BMI) >45 kg/m^2 at screening or currently enrolled in a weight loss program and still in active phase of weight loss, as judged by Investigator.
 

	
 
HbA1c at screening ≥9%
 

Total expected number of patients	A total of ~420 patients are expected (~280 patients will be randomized to alirocumab and ~140 randomized to usual care).
STUDY TREATMENT(s)	
Investigational medicinal product(s)	Alirocumab (open label).
Formulation:	Prefilled pen; Sterile alirocumab drug product supplied at a concentration of 75 mg/mL or 150 mg/mL in histidine, pH 6.0, polysorbate 20, and sucrose.
Route(s) of administration:	Subcutaneous (SC); 1 injection of 1 mL SC in the abdomen, thigh, or outer area of upper arm (ie, deltoid region)
Dose regimen:	Alirocumab 75 mg Q2W with possible uptitration at Week 12 to 150 mg Q2W. The last planned injection of alirocumab IMP is to be administered at Week 22.
	Note: A placebo injection for training purposes will be administered to the patient at screening, with the option of a second training injection prior to randomization. If the person who is designated to administer alirocumab to the patient changes during the course of the study, the new designated person will be trained with a placebo.
Investigational medicinal	Usual Care (open label).
product(s)	There are five options available in the usual care arm including the option to

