## 8.1.1.2 Timing of administration

During the screening period, patients or the designated person will have to perform a placebo self-injection training using a prefilled pen, before randomization and the first alirocumab injection.

At the randomization visit, the first alirocumab injection will be done at the site by the patient or another designated person (such as spouse, relative, etc) under direct site staff supervision. Patients will be monitored at the investigational site for at least 30 minutes after this first injection in this study. If the designated person changes during the course of the study, the new designated person will need to be trained with placebo prior to administering alirocumab to the patient.

Alirocumab SC injections will then be performed outside of the clinic, Q2W up to the last injection. If the injection is scheduled to take place on the same date as the site visit, then alirocumab should be administered after the blood sampling has been completed. In exceptional cases, if a patient prefers to have the injection performed at the study site and provisions are able to be made to accommodate the administration of injections at the site, it may also be allowed.

18-Nov-2015 Version number: 1

Alirocumab should be administered SC Q2W, ideally at approximately the same time of the day; however, it is acceptable to have a window period of  $\pm 3$  days. The time of the day is based upon the patient's preference.

If by mistake or due to other circumstances an injection is delayed by:

- more than 7 days from the missed date or completely missed, then the patient should return to the original schedule of alirocumab administration without administering delayed injections.
- less than or equal to 7 days from the missed date, then the patient should administer the delayed injection and then resume the original schedule of alirocumab administration.

Please note that injections should not be administered within less than 7 calendar days. Please refer to Section 10.4.1.3 for the definition of overdose with alirocumab.

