#### 8.5 PACKAGING AND LABELING

#### 8.5.1 Alirocumab

For the OLTP, each open-label treatment kit will be prepared to contain 6 prefilled pens.

In order to protect the blinding of dose information, treatment kit boxes for injection provided at Week 12 will have the same look and feel and therefore will be labeled with the same label.

In addition to the open-label treatment kits for injection, a training kit containing 1 placebo for alirocumab prefilled pen will be prepared for the purpose of instructing patients on injection administration which is to be performed prior to randomization. If deemed necessary, a second injection training with placebo for alirocumab can be performed using an additional training kit prior to randomization. Injection training with placebo will be performed and documented in the source data and the CRF, including if the designated person who administers alirocumab to the patient changes during the course of the study.

Packaging is in accordance with the administration schedule. The content of the labeling is in accordance with the local regulatory specifications and requirements.

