## 9.2.5.2.1 Sampling time

Serum samples for anti-alirocumab antibodies determination will be drawn periodically throughout the study as per schedule noted in the study flowchart (Section 1.2). All samples will be obtained before alirocumab injection (pre-dose) for patients randomized to alirocumab.

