were up-titrated to 150 mg. These analyses will be exploratory and descriptive (no formal comparison per dose) as it is expected that there could be inherent differences in the baseline characteristics between those patients titrating to 150 mg and those remaining on 75 mg. In order to reduce the bias of this analysis, the period before the up-titration time point (planned at Week 12) will be analyzed separately since only the dose 75 mg is proposed for this time period and consequently the early events occurring before Week 12 can only be attributed to this dose. Therefore the descriptive analysis per dose will include any safety events occurring from the first injection post Week 12 IVRS/IWRS transaction to the end of the TEAE period. Baseline characteristics of patients receiving each dose will be summarized.

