**Table 2 - Analysis windows definition** 

Time point	Targeted study day	Analysis window in study days
Week 4	29	15 to 42
Week 8	57	43 to 70
Week 12	85	71 to 98 for usual care
		71 to minimum (98; study day corresponding to the first injection with
		IMP from kit allocated at up-titration IVRS contact) for alirocumab
		group
Week 20	141	127 to 154
Week 24	169	155 to 182
Week 32	225	211 to 238

Study day is calculated from the day of randomization. Day 1 is the day of randomization.

If multiple valid values of a variable exist within an analysis window, the nearest from the targeted study day will be selected. If the difference is a tie, the value after the targeted study day will be used. If multiple valid values of a variable exist within a same day, then the first value of the day will be selected when time is available, else the scheduled visit will be selected.

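### The split of treatment-emergent ADA by up-titration status has no cut at Week 12, so responses that arose on 75 mg alone are counted in the up-titrated row

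*SAP*

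**What the plan says.** SAP 2.1.10 fixes the sampling: "Anti-alirocumab antibodies (status, neutralizing status and titer) will be collected at Week 0, Week 12, and Week 24". Protocol 9.2.5.2.1 adds: "All samples will be obtained before alirocumab injection (pre-dose) for patients randomized to alirocumab".

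The Protocol summary gives the regimen as "Alirocumab 75 mg Q2W with possible uptitration at Week 12 to 150 mg Q2W". SAP 2.4.3.1 defines an up-titrated patient by the Week 12 IVRS/IWRS transaction plus at least one later 150 mg injection.

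SAP 2.4.8 uses every ADA sample, whatever its timing relative to injections. Among its summaries it counts "patients with treatment-emergent ADA positive response by treatment group, overall and according to up-titration status". It also gives the persistent, transient or intermediate class and the time to onset by the same status. ADA status, neutralizing status and titers are given by time point as well as by status.

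For adverse events, SAP 2.4.5 (General common rules) treats the same split differently. It reasons that "the early events occurring before Week 12 can only be attributed to this dose", analyses that period separately, and starts the per-dose description at the first injection after the Week 12 transaction.

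**The concern.** Up-titration status is a label that a patient acquires at or after Week 12. Treatment-emergent ADA is a whole-study outcome, and one of its two scheduled post-baseline samples is drawn before the label can take effect. Crossing the two without a time limit places antibody responses that came before the dose increase in the row of patients who had the increase.

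The SAP elsewhere describes the split as staying on 75 mg versus going to 150 mg, so a reader of the clinical study report may well take the rows as immunogenicity by dose. Only samples taken after the first injection following the Week 12 transaction can carry information on ADA that arose after the increase. The treatment-emergent incidence and class summaries do not separate those responses from the earlier ones.

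**Working it through.** The documents state no ADA figure, so there is nothing to reproduce. The check is a timeline, followed by a simple product for size.

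**Inputs from the documents**
- ADA samples at Weeks 0, 12 and 24 (SAP 2.1.10; Protocol section 10, Laboratory tests).
- Samples are pre-dose (Protocol 9.2.5.2.1). On a visit day, "alirocumab should be administered after the blood sampling has been completed" (Protocol 8.1.1.2).
- Injections every 2 weeks from Week 0, the last at Week 22; "each open-label treatment kit will be prepared to contain 6 prefilled pens" (Protocol 8.5.1).
- The Week 12 window in the alirocumab arm runs from day "71 to minimum (98; study day corresponding to the first injection with" product from the kit allocated at the up-titration contact (SAP 2.5.3, Table 2). SAP 2.5.3 applies the windows to ADA.
- 280 patients planned in the alirocumab arm (SAP 1.1).

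**Timeline**
- Planned injections: 22/2 + 1 = 12.
- First kit: six pens, Weeks 0, 2, 4, 6, 8 and 10, all 75 mg.
- Second kit: six pens, Weeks 12 to 22, either 75 mg or 150 mg.
- The Week 12 window closes no later than the day of the first injection from the second kit, and on that day blood is drawn first. A Week 12 ADA result therefore follows at most six 75 mg injections and no 150 mg injection.

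**Where a response lands, for a patient who is later up-titrated**

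| First treatment-emergent response | Doses received before it | Row in SAP 2.4.8 |
|---|---|---|
| Week 12 sample | 75 mg only | Up-titrated |
| Week 24 sample | 75 mg, then 150 mg | Up-titrated |

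Under the SAP 2.4.5 rule for TEAEs, an event timed like the first line would be kept out of the per-dose description. That rule is written for TEAEs and safety events. It cannot be read into 2.4.8, which says that all samples are used.

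**Size**

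Let u be the up-titrated share, p the treatment-emergent ADA rate among those patients, and f the share of their responses first seen at Week 12.
- Responders in the up-titrated row: 280 × u × p.
- Of these, arising before up-titration: 280 × u × p × f.
- Fraction of the row affected: f, whatever u and p are.

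The documents give none of u, p or f. The assumed ranges are u 20–50%, p 2–10% and f 25–75%:
- Low: 280 × 0.20 × 0.02 = 1.1 in the row; × 0.25 = 0.3 arose before up-titration.
- Middle: 280 × 0.35 × 0.05 = 4.9; × 0.50 = 2.5.
- High: 280 × 0.50 × 0.10 = 14.0; × 0.75 = 10.5.

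These figures show scale only. The affected fraction simply restates the assumed f.

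**The case against.** **The label is not a dose.** SAP 2.4.8 speaks of up-titration status and makes no claim about immunogenicity at 150 mg. The same bullet splits pre-existing ADA by that status, which no study dose can have caused, so the rows can be read as describing patients. This stands as a limit: the misattribution arises when the row is read as a dose effect. But SAP 2.4.4.2.4 and 2.4.5 describe the split as 75 mg versus 150 mg, and 2.4.5 took the trouble to guard against that reading for TEAEs.

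**Much of the information is already planned.** Status, neutralizing status and titers by visit separate Week 12 from Week 24. With two scheduled post-baseline samples, time to onset clusters near Day 85 and Day 169. This also stands in part. However, status by visit does not separate pre-existing from treatment-emergent ADA, and descriptive statistics of onset do not directly give the two counts. The incidence and class rows remain unsplit.

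**A cut does not isolate dose.** A first positive result at Week 24 follows 75 mg and then 150 mg, in patients selected on their Week 8 non-HDL-C. One scheduled later sample cannot support a persistence class. Both points are right, and they shape the fix.

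**A stronger reading is tempting:** that antibodies blunt the effect, raise Week 8 non-HDL-C and so cause the up-titration. The documents do not support it. No ADA sample is scheduled at Week 8, and no data linking ADA to loss of effect are given. If the association were of interest, it would be a reason to keep the Week 12 responders visible by status rather than drop them.

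**Conclusion.** The point holds as an inconsistency within the SAP. Treatment-emergent ADA incidence, class and time to onset are split by a label set at or after Week 12, using samples that include one drawn before any 150 mg injection. The SAP makes the corresponding cut for TEAEs and not for ADA. The planned by-visit tables and time to onset reduce the problem without removing it.

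The affected fraction equals the share of up-titrated responders first positive at Week 12. That share is unknown, so a reader should not infer that most of the row is misplaced; the documents neither support nor exclude it. Nor do they show that the table would make 150 mg look more immunogenic.

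The conclusion assumes that sampling and dosing follow the schedule. Extra ADA samples drawn for allergic skin events (Protocol 10.6.2.1) may fall on either side of Week 12 and do not change it. The summaries are descriptive: the primary and key secondary tests and the overall ADA incidence are unaffected. The change is worth making because it is cheap and follows the SAP's own reasoning.

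**What to change.** In SAP 2.4.8:

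1. Split the by-status treatment-emergent ADA count into two lines: first positive up to the Week 12 sample (before up-titration), and first positive after the first injection following the Week 12 IVRS/IWRS transaction.
2. For the second line, use as denominator patients with no treatment-emergent response by Week 12, at least one injection after that transaction, and an evaluable later sample. Apply this to both status rows; at present only the up-titrated row implies a post-Week 12 injection. Footnote patients with no evaluable Week 12 sample, because a first positive at Week 24 cannot be placed for them.
3. Keep the overall incidence and the time-to-onset summary as planned.
4. Show the persistent, transient or intermediate class overall only, or footnote that the by-status classes include responses that began before up-titration.
5. State that the by-status comparison is not a randomized dose comparison.

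The cost is SAP wording and revised table shells, from data already collected. The downside is small by-status counts, which should be shown as numbers and not interpreted as rates by dose.
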